15.4. Laboratory Marked Abnormalities Criteria

Table 8 Laboratory Marked Abnormalities Criteria

Category / Analyte	SI Units	Criteria
Chemistry		
Alanine Aminotransferase (SGPT)	U/L	> 3*ULN
Albumin	Kg/m3	< 25
Alkaline Phosphatase	U/L	> 400
Aspartate Aminotransferase (SGOT)	U/L	> 3*ULN
Total Bilirubin	µmol/L	> 1.8*ULN
Blood Urea Nitrogen	mmol/L	> 15
Calcium	mmol/L	< 1.8 > 3.0
Creatinine	µmol/L	> 1.7*ULN
Glucose	mmol/L	< 2.8

Apremilast

Statistical Analysis Plan. Protocol CC-10004-PSOR-020

Amgen INC.

Category / Analyte	SI Units	Criteria
		> 13.9
Hemoglobin A1C	%	> 9
Lactate Dehydrogenase	U/L	> 3*ULN
Magnesium	mmol/L	>1.2
Phosphate	mmol/L	< 0.64 >1.60
Potassium	mmol/L	3.0 5.5
Sodium	mmol/L	< 130 > 150
Triglycerides	mmol/L	> 3.4
Urate	umol/L	Male: > 590; Female: > 480
Hematology		
Hemoglobin	g/L	Female < 8.5, Male < 10.5 Female > 17, Male > 18.5
Leukocytes	10^9/L	< 1.5
Lymphocytes	10^9/L	< 0.8
Neutrophils	10^9/L	< 1.0
Platelets	10^9/L	< 75 > 600
Total cholesterol	mmol/L	> 7.8

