5. TABLE OF EVENTS

Table 3: Table of Events

Visit Number	Screening	Placebo-Controlled Phase ^a					Apremilast Extension Phase ^b				Post-Treatment Observational Follow-up ^d
		1	Baseline 2	3	4	5	6	7	8	9/ET ^c	
Week	-35 to 0 days	0 (Day 1)	2 (± 3 days)	4 (± 3 days)	16 (± 3 days)	20 (± 4 days)	32 (± 4 days)	44 (± 4 days)	52 (± 4 days)		56 weeks (or 4 weeks after study discontinuation)
Informed consent ^e	X	-	-	-	-	-	-	-	-	-	-
Inclusion/Exclusion criteria	X	X	-	-	-	-	-	-	-	-	-
Demographics	X	-	-	-	-	-	-	-	-	-	-
Medical history	X	-	-	-	-	-	-	-	-	-	-
Prior / concomitant medications or therapies	X	X	X	X	X	X	X	X	X		-
Clinical and Laboratory Assessments											
Adverse events ^f	X	X	X	X	X	X	X	X	X	X	
Pregnancy test and contraception education ^g	X	X	-	-	-	-	-	-	X	-	
Vital signs	X	X	X	X	X	X	X	X	X	-	
Height	X	-	-	-	-	-	-	-	-	-	
Weight	X	X	X	X	X	X	X	X	X	-	
Waist Circumference	X	X	X	X	X	X	X	-	X	-	
Body Mass Index	X	-	-	-	-	-	-	-	-	-	
Physical Examination	X	-	-	-	-	-	-	-	-	-	
Clinical laboratory evaluations ^{h,i}	X	X	-	-	X	-	X	-	X	-	

Approved

Table 3: Table of Events (Continued)

Visit Number	Screening	Placebo-Controlled Phase ^a				Apremilast Extension Phase ^b				Post-Treatment Observational Follow-up ^d
	1	Baseline 2	3	4	5	6	7	8	9/ET ^c	
Week	-35 to 0 days	0 (Day 1)	2 (± 3 days)	4 (± 3 days)	16 (± 3 days)	20 (± 4 days)	32 (± 4 days)	44 (± 4 days)	52 (± 4 days)	56 (or 4 weeks after study discontinuation)
Health-related Quality of Life and Efficacy Assessments^j										
DLQI	X	X	X	X	X	X	X	-	X	-
sPGA of Visible Location ^k	X	X	X	X	X	X	X	-	X	-
ScPGA ^k	X	X	X	X	X	X	X	-	X	-
Nail Assessment ^l	X	X	X	X	X	X	X	-	X	-
NAPSI ^k		X	X	X	X	X	X	-	X	-
Modified sPGA-G ^k	X	X	X	X	X	X	X	-	X	-
PPPGA ^k	X	X	X	X	X	X	X	-	X	-
Itch NRS	-	X	X	X	X	X	X	-	X	-
Skin Discomfort/Pain VAS	-	X	X	X	X	X	X	-	X	-
PASI	X	X	X	X	X	X	X	-	X	-
BSA	-	X	X	X	X	X	X	-	X	-
EQ-5D	-	X	-	-	X	-	-	-	X	-
PNQ	-	X	-	-	-	-	-	-	-	-
PBQ	-	-	-	X	X	-	X	-	X	-
WPAI: PSO	-	X	-	-	X	-	-	-	X	-
Photography ^m	-	X	-	-	X	-	X	-	X	-

Approved

Table 3: Table of Events (Continued)

Visit Number	Screening 1	Placebo-Controlled Phase ^a				Apremilast Extension Phase ^b				Post-Treatment Observational Follow-up ^d 56 (or 4 weeks after study discontinuation)
		Baseline 2	3	4	5	6	7	8	9/ET ^c	
Week	-35 to 0 days	0 (Day 1) (± 3 days)	2 (± 3 days)	4 (± 3 days)	16 (± 3 days)	20 (± 4 days)	32 (± 4 days)	44 (± 4 days)	52 (± 4 days)	
Dispense IP	-	X	-	X	X	X	X	X	-	-
Return and Count IP Tablets	-	-	-	X	X	X	X	X	X	-

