- All percentages are rounded to one decimal place. The number and percentage of responses are presented in the form XX (XX.X), where the percentage is in the parentheses, and the 95% CI are presented to two decimal places. Exact 100% that is not rounded from a percent >99.50% is presented in the format xx (100);
- All listings are sorted for presentation in order of treatment arm, study center, subject, and date of procedure or event;
- All analysis and summary tables have the analysis population sample size (i.e., number of subjects);
- All laboratory data will be reported using standard international (SI) units.

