Time points in the analyses or summaries of efficacy data over time include the scheduled study weeks per protocol, the end of a study phase, and the observational follow-up visit. Appropriate dates (e.g., date of measurement or date of specimen collection) will first be used to ensure only data (including data from scheduled, unscheduled, container visits, discontinuation, and observational follow-up visits) measured or collected within the specific analysis phase (as defined in Section 5.2) being analyzed or summarized are included, and then the visits/study weeks as recorded in the database will be used to assign one value (possibly missing) to each time point at the subject level. It is possible that multiple assessment values will fall into the same visit window. The following rule may be used to select the unique value for that analysis visit:

1. Among all assessments in the same visit window for the analysis visit, select the value with the assessment date closest to the target day of the analysis visit;
2. If the relative days from 2 assessments are equally close to, but on different sides of the target day, then the latter assessment will be used for that analysis visit;
3. If multiple assessments are available on the same relative day, then the highest value of these assessments will be used for that relative day.

The time points for summaries of safety data (laboratory parameters, vital signs and weight) are based on study week/visit for the placebo-controlled phase. For the Apremilast Exposure Period, the scheduled study weeks for placebo subjects who are treated with Apremilast 30 mg BID at Week 16 will be mapped to reflect the study weeks relative to the first dose of Apremilast (see table below).

Table 3: Adjustment and Mapping of Study Weeks for Placebo Subjects who are Treated with Apremilast 30 mg BID after Week 16 in Summary of Safety Data over Time

Original Visit	Re-Mapped Visit for subjects initially randomized to placebo
Week 16	Baseline
Week 20	Week 4
Week 32	Week 16
Week 44	Week 28
Week 52	Week 36

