10. SAFETY ANALYSIS

Safety will be assessed via descriptive statistics and point estimates on observed data.

All safety analyses described in this section will be performed for both the Placebo-controlled Phase and the Apremilast Exposure Period. The safety analyses for the Placebo-controlled Phase will be based on the safety population and presented by treatment arm (placebo, and Apremilast 30 mg BID). The safety analyses for the Apremilast Exposure Period will be based on the Apremilast Exposure Population and presented by Apremilast dose group (i.e., Apremilast 30 mg BID) irrespective of the start time of Apremilast exposure (at Week 0 or 16). In addition, selected summaries on AEs for the Observational Follow-up Phase will be listed.

For the analyses of AEs and laboratory marked abnormalities, both subject incidence and exposure-adjusted incidence rate (EAIR) per 100 subject-years for the Placebo-controlled Phase (Weeks 0 to 16) and for the Apremilast Exposure Period will be provided. The point estimates of subject incidence and EAIR are distinguished as following:

- Subject incidence: is defined as the number of subjects with the specific event divided by the number of subjects included in the analysis (i.e., percentage [%] used in a frequency summary). Subjects with multiple occurrences of the specific event in the specific analysis period will be counted only once in the numerator.
- Exposure-adjusted incidence rate (EAIR) per 100 subject-years: The EAIR per 100 subject-years is defined as 100 times the number of subjects with the specific event divided by the total exposure time (in years) among subjects included in the analysis. Subjects with multiple occurrences of the specific event in the specific analysis period will be counted only once in the numerator. The exposure time for a subject without the specific event is the treatment duration (i.e., last dose date-first dose date+1), whereas the exposure time for a subject with the specific event is the treatment duration up to the start date (inclusive) of the first occurrence of the specific event. The total exposure time in years is calculated by dividing the sum of exposure time in days over all subjects included in the analysis by 365.25. The EAIR per 100 subject-years is interpreted as the expected number of subjects with at least one occurrence of the specific event per 100 subject-years of exposure to the IP.

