10.2. Clinical Laboratory Evaluations

The endpoints for clinical laboratory evaluations include:

- Laboratory marked abnormalities (see [section 15.4](#))
- Observed value and change from baseline over time in the following laboratory parameters
 - Hematology panel including complete blood count (CBC) with differential, including red blood cell (RBC) count, hemoglobin, hematocrit, mean corpuscular hemoglobin (MCH), mean corpuscular hemoglobin concentration (MCHC), RBC Morphology, mean corpuscular volume (MCV), white blood cell (WBC) count (with differential), and platelet count.
 - Chemistry panel including sodium, potassium, calcium, chloride, blood urea nitrogen (BUN), creatinine, creatinine clearance, glucose, albumin, total protein, alkaline phosphatase, bilirubin (total and direct), aspartate aminotransferase/serum glutamic oxaloacetic transaminase (AST/SGOT), alanine aminotransferase/serum glutamic pyruvic transaminase (ALT/SGPT), gamma-glutamyl transferase (GGT), lactate dehydrogenase (LDH). A lipid panel will be included in the standard chemistry panel.
- Shifts from baseline to post-baseline time points and to the worst post-baseline value in terms of normal/abnormal (low or high) in the above hematology and serum chemistry parameters. Normal range will be used to determine the categories of High, Low, and Normal for lab tests.

Summary statistics (N, Mean, STDEV, Median, Minimum, and Maximum) of observed values and changes from baseline in laboratory parameters will be provided over time by scheduled visit and

Apremilast**Statistical Analysis Plan. Protocol CC-10004-PSOR-020****Amgen INC.**

for the end of Phase/Period assessment. Frequency summaries (shift tables) of shifts from baseline to post-baseline time points and to the worst post-baseline value during the given study phase/period in terms of normal/abnormal will be provided.

Laboratory marked abnormalities will be summarized; subject incidence and EAIR for each abnormality will be calculated based on subjects with a baseline value and at least one post-baseline value for criteria requiring baseline or subjects with at least one post-baseline value for criteria not requiring baseline. A subject data listing of laboratory marked abnormalities during the Placebo-controlled Phase and the Apremilast Exposure Phase will be presented.

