Laboratory marked abnormalities will also be summarized for subjects with normal values at baseline and for subjects with abnormal values at baseline separately. For the purposes of these summaries, subjects with abnormal (normal) values at baseline are defined as those whose baseline value is low (not low) for criteria concerning low values and those whose baseline value is high (not high) for criteria concerning high values; both low and high are relative to the laboratory normal range.

A subject data listing of all laboratory data, including Pregnancy test, with abnormal flags and study phase/period flags will be provided.

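### SAP Table 8 sets haemoglobin limits in g/L that look like g/dL numbers, so every subject tested after baseline would be flagged high and none low

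*SAP*

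**What the plan says.** Table 8 in SAP 15.4 has a column for SI units and a column for criteria. The haemoglobin row has the unit g/L and the criteria "Female < 8.5, Male < 10.5 Female > 17, Male > 18.5". The first pair are the low limits and the second pair the high limits. SAP 5.1 adds: "All laboratory data will be reported using standard international (SI) units". Neither document mentions g/dL, a conversion factor or any other haemoglobin limits.

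The limits feed several outputs in SAP 10.2. "Laboratory marked abnormalities will be summarized; subject incidence and EAIR for each abnormality will be calculated", using subjects with at least one post-baseline value when the criterion needs no baseline. "Laboratory marked abnormalities will also be summarized for subjects with normal values at baseline and for subjects with abnormal values at baseline separately", and a subject listing of marked abnormalities is also planned. These outputs cover the Placebo-controlled Phase and the Apremilast Exposure Period.

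For the exposure-adjusted incidence rate (EAIR), SAP 10 says that "the exposure time for a subject with the specific event is the treatment duration up to the start date (inclusive) of the first occurrence". Protocol Table 3 schedules the laboratory tests at Screening and Weeks 0, 16, 32 and 52.

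**The concern.** A threshold works only if it is on the same scale as the data. Haemoglobin reported in g/L, as SAP 5.1 requires, would be compared with limits of 8.5 to 18.5, which are about a tenth of the size of ordinary adult values on that scale. Everyone would cross the high limit and nobody the low one.

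At stake are the haemoglobin rows of the marked-abnormality incidence and EAIR tables. A real fall in haemoglobin would not appear there as a low flag, and every subject would appear as a high flag. SAP 2 says the plan is to be signed before the Week 16 data transfer so that methods are fixed before unblinded data are seen, and SAP 4.3 allows Week 16 results to be published before the study ends. A limit corrected after that point would no longer be pre-specified.

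**Working it through.** The plan gives no figure to reproduce here, so the check applies the printed limits directly.

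**Inputs**
- Unit g/L; low limits 8.5 (F) and 10.5 (M); high limits 17 (F) and 18.5 (M): SAP Table 8.
- Laboratory data in SI units: SAP 5.1.
- Target days: Week 16 = Day 113, Week 32 = Day 225: SAP 5.5, Table 2.
- Visit windows: ±3 days at Week 16 and ±4 days at Week 32: Protocol Table 3. Protocol 6.2 instead gives ±4 days for Visits 5 to 9, which includes Week 16.
- Haemoglobin values: **assumption**, 60 to 200 g/L. The documents give no range.

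**Step 1: the limits as written.** With 1 g/dL = 10 g/L, the printed limits equal 0.85 (F) and 1.05 (M) g/dL for low, and 1.7 (F) and 1.85 (M) g/dL for high. Only values of 8.5 to 17 g/L in women, or 10.5 to 18.5 g/L in men, would escape a flag.

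**Step 2: ratio of value to limit**

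| Value (g/L) | ÷ 17 (F high) | ÷ 18.5 (M high) | ÷ 8.5 (F low) | ÷ 10.5 (M low) |
|---|---|---|---|---|
| 60 | 3.53 | 3.24 | 7.06 | 5.71 |
| 200 | 11.76 | 10.81 | 23.53 | 19.05 |

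All ratios exceed 1, so every value is above its high limit and none is below its low limit.

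**Step 3: sensitivity to the assumption.** Single values from 30 to 220 g/L give the same flags in both sexes. Under normal distributions with mean 120, 135 or 150 g/L and SD 10, 15 or 20 g/L, P(high) = 1.000000 to six decimals and P(low) is at most 2.2 × 10⁻⁸.

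**Step 4: what the EAIR would show.** Suppose every subject takes a first dose on Day 1, stays on treatment, and is first flagged at the first scheduled post-baseline test.
- Week 16, both arms: 100 × 365.25 / 113 = 323.2 per 100 subject-years. Three days early or late: 365.25 / 110 gives 332.0 and 365.25 / 116 gives 314.9. With a 4-day window: 335.1 (Day 109) and 312.2 (Day 117).
- Placebo subjects who switch: their weeks "will be mapped to reflect the study weeks relative to the first dose of Apremilast", so Week 32 becomes Week 16. Exposure is 225 − 113 + 1 = 113 days, again 323.2. With windows of 3 and 4 days, exposure is 106 to 120 days, giving 344.6 to 304.4. With 4 days at both visits, it is 105 to 121 days, giving 347.9 to 301.9.

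All the variation in this rate comes from the visit date.

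**Step 5: if the printed numbers are g/dL.** Multiplying by 10 gives 85 (F) and 105 (M) for low, and 170 (F) and 185 (M) for high, in g/L. Under the distributions of Step 3, P(high) is then 0.00 to 0.16 (F) and 0.00 to 0.04 (M), and P(low) is 0.00 to 0.04 (F) and 0.00 to 0.23 (M). The flags would separate subjects again.

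**The case against.** - **The practical harm is small.** This stands. A row with 100% high and 0% low would be noticed at the first output review. The shift tables rest on a different rule, "Normal range will be used to determine the categories of High, Low, and Normal for lab tests", and the observed-value and change-from-baseline summaries and full laboratory listing do not use Table 8 either. Safety is descriptive (Protocol 9.7), and no efficacy or treatment rule refers to the table.
- **Some of the outputs keep some content.** This partly stands. The baseline split uses the laboratory normal range, so its group sizes would still show how many subjects started outside it, although both groups would be 100% high. The subject listing would be over-inclusive for haemoglobin; any values it printed would still be readable. It is the incidence and EAIR rows that lose their meaning.
- **The figure of 323 is hypothetical.** This stands. Early terminations, for which SAP 4.4 allows 24% before Week 16, and unscheduled tests would bring earlier flags and higher rates. SAP 5.2.1 also ends the Placebo-controlled Phase the day before the first apremilast dose dispensed at Week 16, so on a strict date reading an on-schedule sample could fall outside the phase. The 100% and 0% among subjects with a post-baseline value depend on none of this.
- **A character may have been lost in the PDF text.** This cannot be fully excluded; the potassium row nearby has lost or lacks its comparison signs. But all four haemoglobin limits are intact and on one scale, and g/L agrees with the column heading and SAP 5.1. Had the unit been g/dL, the limits would still have to be reconciled with the SI rule.
- **The documents do not show which entry is wrong.** This stands. The SI rule favours keeping g/L but does not establish the intended limits. The albumin row, below 25 kg/m³ (that is, 25 g/L), shows only that the table uses this mass scale elsewhere.

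**Conclusion.** The concern holds, as a minor one. As written, the haemoglobin criterion flags 100% of subjects with a post-baseline value as high and 0% as low, in both arms of the Placebo-controlled Phase and in the single-arm Apremilast Exposure Period. The only outside assumption needed is that haemoglobin exceeds 18.5 g/L in men and 17 g/L in women; the range of 60 to 200 g/L used for the ratios is far from those values. That the printed numbers are g/dL is an inference from their scale. The mismatch between unit and limits does not depend on that inference.

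**What to change.** Before programming, the sponsor should confirm the intended haemoglobin limits and restate them in g/L in Table 8, so that the row agrees with SAP 5.1. If the printed numbers prove to be g/dL, the g/L limits are those in Step 5. If they came from another source, the confirmed values should replace them. The cost is one table row in the SAP and the matching line of code. It needs no new data and changes no other analysis.
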